2.2 Analysis Populations

The following analysis populations will be defined for the study:

Safety Analysis Population: The safety population will consist of all patients who have received at least one administration of the study treatments, whether prematurely withdrawn from the study or not. For the safety analysis population, data will be analyzed according to the treatment actually taken.

Pharmacokinetic (PK) Analysis Population: The PK population will consist of all patients with at least one administration of the study treatments, and with at least one sample collected and analyzed for plasma drug concentration, whether prematurely withdrawn from the study or not.

Exploratory Analysis Population: The Exploratory population will consist of all randomized patients who meet the inclusion/exclusion criteria, received full-course of the study drug as per randomization, have completed the main relevant visits and without any major protocol violations which would render the data unreliable.

Analyses of safety will be performed on the Safety population, as will baseline patient characteristics and demographics. Analysis of PK variables will be performed on the PK population. Analyses of PD data will be performed on the Exploratory population. Prior to the final analysis, a blinded review of the protocol violations will be held in order to determine exclusions from the Exploratory population.

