If a patient experiences an AE that is judged to be related to the study drug, and is graded as mild or moderate, the patient may receive a further dose of study drug following discussion with the investigator and sponsor, dependent on the nature of the AEs reported. Expected transient GI pain requiring 48 hours stop and not resuming with reinitiation of treatment is commonly observed. The number of subjects reporting similar AEs and reports of the same or similar AEs in a patient, will form part of the assessment to determine if patients should be re-challenged.

Changes in vital signs and ECG intervals

Patients will be discontinued if after repeated measurements, have pulse/heart rate, blood pressure or ECG interval measurements that fulfil one or more of the criteria listed below.

Vital signs

- Pulse/heart rate <40 or >120 beats per minute (BPM)
- Systolic BP <90 or >180 mm Hg
- Diastolic BP <50 or >100 mm Hg

Laboratory tests

- Severe hypokalemia (defined as less than 2.5 mEq/L) or persistent hypokalemia despite potassium supplementation
- Thrombocytopenia is defined as meeting one or both criteria:
 - Platelet count below $150 \times 10^9/L$ (or 150.000 platelets per microliter (mcL))
 - Platelet count drop of $\geq 50\%$ compared to baseline
- Severe drug-induced liver injury (DILI).
- Dehydration and orthostasis (defined by a fall in systolic blood pressure over 20 mm Hg or a fall in diastolic pressure over 10 mm Hg within 3 minutes of standing).

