3.2.1 RATIONALE FOR DOSAGE SELECTION AND TREATMENT DURATION

As [REDACTED] is expected to be the main driver of the STP1 effect, only the dose of [REDACTED] will be increased between the two cohorts while the dose of [REDACTED] will be fixed to [REDACTED] twice a day (6 hours apart).

The starting dose of [REDACTED] mg of [REDACTED] twice a day (6 hours apart) was chosen based on the PK and safety data available from the literature. The margins of safety (MOS) associated with the starting dose is [REDACTED] and was derived from the preclinical toxicokinetic data and the estimated NOAEL in the toxicology studies performed in the dog, the most sensitive species to STP1. The second dose level of [REDACTED] mg twice a day (6 hours apart) is expected to allow [REDACTED] to reach a C_{trough} of approximately 13 ng/mL, corresponding to 56 nmol which is within the range of PDE4 IC₅₀ [Huang et al, 2006]. Hence, the 5 and 10 mg twice a day (6 hours apart) doses are expected to modulate PDE4 and might already show positive PD effects (e.g., on EEG endpoints or on processing speed, as assessed by a computerized cognitive battery). The safety / tolerability profile should remain acceptable as per extensive data collected in [REDACTED] and from clinical trials and summarized in Table 1, with nausea as the most frequent AE reported with doses of 30 mg/day. In this study, the maximum dose planned is 20 mg/day for 2 weeks.

[REDACTED] alone given to children and adolescents with ASD, aged 2 to 18 years, has been shown to improve core symptoms in a subset of patients with an acceptable risk/benefit ratio at a dose of 1 mg twice a day (6 hours apart) for 3 months [Lemonnier et al, 2017].

The [REDACTED] steady state concentration should be achieved after 4 days of treatment. Hence, a 2-week treatment duration with STP1 was considered appropriate to provide sufficient safety, tolerability and PK information for both [REDACTED], after multiple dosing of STP1. Beneficial impacts of PDE4 inhibitors on cognition, and more specifically processing speed, have been recently described in different studies involving healthy volunteers [Chiu et al, 2014; Heckman et al, 2018; Van Duinen et al, 2018]. Two weeks of treatment are thought to be sufficient to observe potential PD

effects on EEG recordings, or cognition and processing speed (as assessed by the [REDACTED] or KiTAP test battery).

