- **Subject Medication Diary**

All enrolled (i.e., randomized patients) will be asked to maintain a "Subject Medication Diary". This template diary will be provided during the Baseline/Randomization visit to keep track of the daily doses and of the timing of study medications. Patients will be asked to bring this diary along with the study medication bottles to the Day 7 and Day 14 study visits to assess for compliance and drug accountability. If this is not done at the Day 14 visit for any reason, this can also be completed at Day 28 visit.

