6.3.3 PHARMACOKINETIC ANALYSIS POPULATION

All patients who have received at least one administration of the study treatments and with at least one sample collected and analyzed for plasma drug concentration, whether prematurely withdrawn from the study or not, will be included in the PK analysis.

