5.0 Analysis of Pharmacokinetics

5.1 Description of Pharmacokinetic Variables

PK sampling will be collected from all patients for measurement of plasma and urine concentrations of ibudilast and bumetanide.

Blood samples will be drawn on Days 1, 7, 14/15 and, optionally, between Days 16 to 18, and urine samples will be collected on Days 1 and 14 to determine concentrations of ibudilast and bumetanide. Non-compartmental analysis (NCA) will be utilized to analyze data from the sampling schema. See Table 1 for the PK sample schedule.

Table 1. PK Sampling Schedule

PK Schedule ^c		
Time	Plasma ^a	Urine ^b
Day 1	0.25, 0.5, 1, 2, 4, and 6h post-AM dose	0 to 6h post-AM dose
Day 7	Pre-AM dose	
Day 14 (only AM dose) and 15	Pre-AM dose and 0.25, 0.5, 1, 2, 4, 6, 8, 10, 12 and 24h post-AM dose	0 to 4h, 4 to 8h, and 8-12h post-AM dose
Between Days 16 to 18 ^d	48, 72, and 96 h post-AM dose of Day 14	

^a Both ibudilast and bumetanide will be analyzed from the same blood draw for each specified sampling time point.
^b Urine creatinine from the urine collection will be paired with a serum creatinine measurement to evaluate completeness of collection.
^c All of these timepoints have a 5-minute window.
^d Optional

The following PK plasma parameters will be estimated for each patient(as far as possible):

PK Parameter	Definition
$C_{max, Day 1}$	Maximum plasma concentration on Day 1
$C_{max,ss}$	Maximum plasma concentration at steady state
C_{Last}	Last measured plasma concentration following the last administration
C_{trough}	Minimum observed plasma concentration prior to drug administration
T_{max}	Time of maximum observed plasma concentration; if it occurs at more than one time point, T_{max} is defined as the first time point with this value
$t_{1/2}$	Terminal elimination half-life, calculated as $\ln(2)/\lambda_z$
AUC_{0-last}	Cumulative area under the plasma concentration time curve calculated from 0 to the last measured plasma concentration following the last administration using the linear trapezoidal method
$AUC_{0-tau (6h), Day 1}$	Area under the plasma concentration time curve to the end of the dosing period following the first administration
$AUC_{0-tau (6h), SS}$	Area under the plasma concentration time curve to the end of the dosing period (6h) following the last administration
$AUC_{0-12h, SS}$	Area under the plasma concentration time curve to 12 hours post dose following the last administration

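### The PK population has no compliance or recent-dosing condition, so an ibudilast Day 14 profile taken soon after a 48-hour treatment stop could be summarised as steady state

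*SAP*

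**What the plan says.** SAP 2.2 sets the entry rule for all PK analyses: "The PK population will consist of all patients with at least one administration of the study treatments, and with at least one sample collected". The sample must also have been assayed for drug in plasma, and patients who withdrew early are included. Protocol 6.3.3 has the same rule: "All patients who have received at least one administration of the study treatments and with at least one sample collected and analyzed for plasma drug".

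The same SAP section treats dosing differently for the exploratory scales. That population must have "received full-course of the study drug as per randomization", and "a blinded review of the protocol violations will be held in order to determine exclusions from the Exploratory population". Neither safeguard is extended to PK.

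On interruptions, the individual stopping rules in protocol 3.1.2 state: "Expected transient GI pain requiring 48 hours stop and not resuming with reinitiation of treatment is commonly observed". On recovery time, protocol 3.2.1 says that the "steady state concentration should be achieved after 4 days of treatment".

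SAP 5.1 gives Day 14 parameters steady-state labels. Cmax,ss, for example, is the "Maximum plasma concentration at steady state". It forms the accumulation ratios by dividing Day 14 AUC0-6 and Cmax by their Day 1 values. SAP 5.2 summarises all of these by treatment group with mean, SD, CV%, geometric mean and 90% CI, in Table 34 for ibudilast and Table 35 for bumetanide.

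**The concern.** The protocol foresees treatment stops of two days and states that about four days of dosing are needed to reach steady state. The SAP does not connect the two. A patient who restarts shortly before Day 14 and gives the full set of samples yields parameters that can be calculated without difficulty. They describe partial re-accumulation but are tabulated as steady state.

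Plasma PK of the combination is the secondary objective. Protocol 3.2.3 uses these data for comparison with published PK, for the choice of Phase 2 dose levels, and to explore whether the diuretic alters the other drug's PK and excretion. Protocol 1.5.2 anticipates that such an effect would appear as a lower plasma level. An unflagged interruption also lowers ibudilast level and could be mistaken for that effect. With at most six active patients per dose level, and as few as three at the highest dose, one profile can move a group mean.

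**Working it through.** **Inputs**
- Half-life about 19 h and Tmax about 4 to 5 h (protocol 1.4.1). I use 4.5 h.
- The other drug: half-life 1 to 1.5 h, Tmax 0.5 to 2 h (protocol 1.4.1).
- Dosing: two doses 6 h apart on Days 1-13, morning only on Day 14, so 13 × 2 + 1 = 27 doses (protocol synopsis).
- Active patients per dose level: up to 6 (protocol 6.1). Minimum at the highest dose: 3 (protocol synopsis).

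The drug name is redacted in these PK paragraphs. I match 19 h to ibudilast and the short half-life to bumetanide, because the latter is described as the diuretic.

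**Step 1: reproduce the plan's own figure.** Five half-lives are 5 × 19 = 95 h, or 3.96 days. At 96 h, 1 − 2^(−96/19) = 97.0% of steady state is reached. The stated 4 days is consistent with this.

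**Step 2: model.** ke = ln 2 / 19 = 0.0365 per h. Solving ln(ka/ke)/(ka − ke) = 4.5 gives ka = 0.69 per h. The concentration at time t is the sum, over doses taken, of [ka/(ka − ke)] × [exp(−ke·u) − exp(−ka·u)], where u is the time since that dose. I remove all doses on two consecutive days and compare Day 14 with uninterrupted dosing.

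**Step 3: ibudilast results.** With no interruption, AR_AUC is 3.18 and AR_Cmax is 2.75.

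| Days missed | AUC0-6, share of uninterrupted | Trough, share | AR_AUC |
|---|---|---|---|
| 12-13 | 43% | 17% | 1.38 |
| 11-12 | 76% | 66% | 2.43 |
| 10-11 | 90% | 86% | 2.87 |
| 9-10 | 96% | 94% | 3.05 |
| 8-9 | 98% | 98% | 3.13 |

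Stops on Days 6-7 or earlier leave about 100%.

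**Step 4: sensitivity.** I vary the half-life over 15 to 24 h (an assumed range) at Tmax 4.5 h, and Tmax over 4 to 5 h at 19 h. The AUC share is then 42-45% for Days 12-13, 72-82% for Days 11-12, 86-94% for Days 10-11 and 93-98% for Days 9-10.

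**Step 5: effect of one Days 12-13 case on a group summary.**
- Geometric mean AUC: 0.433^(1/6) = 0.870, a fall of 13% at n=6. 0.433^(1/3) = 0.757, a fall of 24% at n=3.
- Arithmetic mean AUC: (1 − 0.433)/6 = 9.4% and (1 − 0.433)/3 = 18.9%.

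**Step 6: bumetanide.** With half-life 1.25 h and Tmax 1 h, or 1.5 h and 2 h, AUC0-6, Cmax and both ratios stay at 1.00 even after a Days 12-13 stop. Only the pre-dose trough changes, and it is already near zero.

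**Step 7: with a four-day condition.** If all doses on Days 10-13 were taken, the worst two-day stop still unflagged is Days 8-9, at 98% of the uninterrupted AUC. One such patient among six lowers the mean by 0.3%.

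**The case against.** **The large shifts come from the worst case.** Of the 12 possible two-day windows in Days 1-13, nine leave Day 14 AUC0-6 at 96% or more. Only Days 11-12 and 12-13 cost clearly more than 10%. This stands and limits the point to restarts close to Day 14.

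**How often it would happen is unknown.** The basis is one loosely worded sentence. The ibudilast experience in protocol 1.4.2 suggests modest GI rates: nausea 0.56% and anorexia 0.58% in about 15,000 patients, and GI effects of 11.2% and 2.3% in two studies at 30 mg/day. The maximum here is 20 mg/day. A reader might infer that such profiles will enter the means. The documents do not support that, since they give neither rate nor timing, and a patient who withdraws before Day 14 adds no Day 14 profile.

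**Some of it would be visible.** Individual parameters (DL17), deviations (DL37) and individual concentration plots (Figures 14-21) are planned. They would help a careful reader, but they do not correct the tabulated means. The SAP 5.1 wording about estimating parameters as far as possible concerns whether a value can be calculated, and an interrupted profile can be.

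**Excluding patients has its own cost.** No passage links intolerance to higher or lower exposure. If patients who interrupt are those with high exposure, dropping them would bias the summary downward. Precision also suffers: the 90% CI half-width is t(0.95, n−1)/√n SDs, which is 2.920/√3 = 1.69 at n=3 and 6.314/√2 = 4.46 at n=2. This stands, and it argues for a second summary beside the first, not for exclusion.

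**Conclusion.** The gap is real and confined to ibudilast. No rule in either document keeps a Day 14 profile taken within about two days of a restart out of the steady-state rows and accumulation ratios of Table 34. If a patient stopped on Days 12-13, that profile would show less than half of the uninterrupted AUC and an accumulation ratio of 1.38 in place of 3.18. This is enough to distort a group of three to six. Stops that end by Day 10 cost about 4% or less at a 19 h half-life, and up to 7% at 24 h.

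Three stronger readings fail. The PK rule does contain a dosing condition, namely one administration. What it lacks is a compliance or recent-dosing condition. The bumetanide AUC, Cmax and ratios are not affected. And the plan allows the problem without making it certain.

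The figures assume linear one-compartment kinetics. They also assume that the half-life and Tmax quoted for a delayed-release product hold for the trial's formulation.

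**What to change.** Add to SAP 5.2, for ibudilast and Table 34 only:

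- Before unblinding, flag each Day 14 profile with any missed dose on Days 10-13 (the protocol's own four days) or with a Day 14 morning dose that was not retained. Use the diary, the eCRF dose times and drug accountability.
- Present the steady-state parameters and both accumulation ratios for unflagged profiles alongside the all-patient summary.
- Show the flag in DL15 and DL17.

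Leave the PK population, the Day 1 summaries, the bumetanide tables and the exposure-AE exploration as they are. This is an analysis rule and changes nothing in patient management.

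**Cost.** It takes SAP wording, one extra summary block and some data entry. The diary exists to "keep track of the daily doses and of the timing of study medications", but protocol 4.6.1.6 sends only the afternoon dose times of Days 6 and 13 to the eCRF. DL34 lists morning doses by visit, and DL35 gives pill counts and a taken-as-directed item. Diary entries for Days 10-12 may therefore need transcription. The unflagged n may fall, and at the minimum of three patients its 90% CI may be very wide or not estimable. The threshold is also somewhat blunt: a single missed dose on Day 10 still leaves AUC at about 98% yet is flagged. Because nothing is removed from the all-patient summary, that costs little.

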Sample size	
The target number of completers for this Phase 1b study is up to 16 ASD-Phen1 individuals. Assuming a dropout rate of approximately 20%, the proposed sample size is up to 20 patients to be randomized. This sample size should provide the first evidence of safety, tolerability and pharmacokinetics of STP1 in individuals with ASD-Phen1 to inform potential future studies.

TABLE OF CONTENTS

SECTION 4.3 - METHOD OF TREATMENT ASSIGNMENT AND BLINDING	6
SECTION 11 - APPENDIX 1 SCHEDULE OF ASSESSMENTS – SRS-2.....	8
1. INTRODUCTION	29
1.1 BACKGROUND ON THE DISEASE	29
1.2 STRATIFICATION AND THERAPEUTIC STRATEGIES	29
1.2.1 CLINICAL SIGNS AND SYMPTOMS OF ASD-PHEN1	30
1.2.2 RATIONALE FOR STP1	31
1.3 NON-CLINICAL EXPERIENCE.....	32
1.3.1 NON-CLINICAL PHARMACOLOGY.....	32
1.3.2 NON-CLINICAL PHARMACOKINETICS AND METABOLISM.....	33
1.3.3 TOXICOLOGY, SAFETY PHARMACOLOGY AND GENOTOXICITY.....	35
1.4 PREVIOUS CLINICAL EXPERIENCE.....	37
1.4.1 CLINICAL PHARMACOKINETICS.....	37
1.4.2 SAFETY AND TOLERABILITY.....	38
1.5 STUDY RATIONALE AND BENEFIT-RISK ASSESSMENT	42
1.5.1 STUDY RATIONALE.....	42
1.5.2 BENEFIT-RISK ASSESSMENT.....	42
2. OBJECTIVES OF THE STUDY	45
2.1 PRIMARY OBJECTIVE.....	45
2.2 SECONDARY OBJECTIVE.....	45
2.3 EXPLORATORY OBJECTIVES	45
3. INVESTIGATIONAL PLAN	46
3.1 STUDY DESIGN	46
3.1.1 OVERVIEW OF STUDY DESIGN	46
3.1.2 STOPPING RULES	47
3.1.3 DATA SAFETY MONITORING BOARD (DSMB)	48
3.1.4 END OF STUDY	50
3.2 RATIONALE FOR STUDY DESIGN	50
3.2.1 RATIONALE FOR DOSAGE SELECTION AND TREATMENT DURATION.....	50
3.2.2 RATIONALE FOR STUDY POPULATION	51
3.2.3 RATIONALE FOR PHARMACOKINETIC SAMPLING	51
3.2.4 RATIONALE FOR BIOMARKER ASSESSMENTS	51
3.3 OUTCOME MEASURES.....	52
3.3.1 SAFETY OUTCOME MEASURES	52
3.3.2 PHARMACOKINETIC OUTCOME MEASURES	52
3.3.3 EXPLORATORY OUTCOME MEASURES.....	53
4. MATERIALS AND METHODS.....	54
4.1 CENTER	54
4.2 STUDY POPULATION.....	54
4.2.1 RECRUITMENT PROCEDURES.....	54
4.2.2 INCLUSION CRITERIA.....	54
4.2.3 EXCLUSION CRITERIA	56
4.3 METHOD OF TREATMENT ASSIGNMENT AND BLINDING.....	57

4.4	INVESTIGATIONAL MEDICINAL PRODUCTS.....	58
4.4.1	FORMULATION, PACKAGING AND HANDLING	58
4.4.2	DOSAGE, ADMINISTRATION AND COMPLIANCE.....	58
4.4.3	INVESTIGATIONAL MEDICINAL PRODUCTS ACCOUNTABILITY.....	58
4.4.4	POST-TRIAL ACCESS TO STP1	59
4.5	CONCOMITANT THERAPIES AND FOOD	59
4.5.1	PROHIBITED THERAPIES.....	60
4.5.1.1	POTENTIAL INTERACTIONS WITH [REDACTED]	60
4.5.1.2	POTENTIAL INTERACTIONS WITH [REDACTED]	60

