3.1.2 STOPPING RULES

Study Stopping rules

During and after the administration of STP1, the patient will be closely monitored for clinically significant signs and symptoms potentially related to the study drugs (ibudilast and bumetanide), in particular for signs and symptoms GI and dehydration and for clinically significant changes in the electrocardiogram (ECG). Any AE should be followed up until resolution. If not resolved, STALICLA shall be contacted and the patient may be considered to withdrawn from the trial depending on the severity of the event/s.

The DSMB will perform reviews of safety data throughout the study.

Enrolment in the study will be placed on hold and no further dosing will occur pending a full safety review if:

- One fatal or life-threatening SAE occurs, that is considered by the investigator as potentially or possibly related to SPT1 and later confirmed the patient received investigational medicinal product (IMP).
- STALICLA, investigators and/or the DSMB considers that the number and/or severity of AEs, abnormal safety monitoring tests or abnormal laboratory findings justify putting the study on hold. Examples are:
 - One severe systemic-related reaction occurs and does not resolve within 24 hours.
 - Three or more similar severe AEs occur as defined by the Common Terminology Criteria for Adverse Events (CTCAE v5.0), which are judged related to STP1.

- If 2 patients at any dose level discontinue treatment due to changes in vital signs, ECG intervals or findings on continuous ECG monitoring no further patients will be enrolled at this dose level pending review by DSMB.

The DSMB can recommend (i) for the study to continue without amendment, (ii) to continue the study with modifications to the protocol or (iii) to stop the study.

The study may continue after the safety review, if the DSMB and STALICLA agree it is safe to proceed.

Individual stopping rules

If a patient experiences an AE following administration of study drug (i.e., post-treatment) that is judged to be related to the study drug, and is graded as severe or SAE, no further doses of study drug will be administered.

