6.3.2 EFFICACY ANALYSIS POPULATION

This study has not been designed for efficacy analysis, but exploratory endpoints will be analyzed to look at early efficacy and/or to allow selection of relevant endpoints for a Phase 2 study. The efficacy population will consist of all randomized patients who meet the inclusion/exclusion criteria, received full course of the study drug as per randomization, have completed the main relevant visits and without any major protocol violations which would render the data unreliable.

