2.3 Missing Data Conventions

No missing value imputation will be used. That is, all analyses will be based on the observed data (i.e., complete case analysis).

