27	Coagulation Results Shift Table by Visit and Clinical Significance (Safety Population)	X	
28	Quantitative Urinalysis Results Shift Table by Visit and Clinical Significance (Safety Population)	X	
29	Blood Chemistry Results for Electrolytes Shift Table by Visit and Clinical Significance (Safety Population)	X	
30	Blood Chemistry Results for Electrolytes Shift Table by Visit and Range of Normal Results (Safety Population)	X	X
31	Number and Proportion of Patients with Blood Chemistry Results for Electrolytes Outside of Normal Range (Safety Population)	X	X
32	Summary Statistics of Ibudilast and Bumetanide Plasma Concentration Levels by Treatment, Visit and Time (PK Population)	X	X
33	Summary Statistics of Ibudilast and Bumetanide Urine Concentration Levels by Treatment, Visit and Time (PK Population)	X	X
34	Summary Statistics of Estimated PK Plasma Parameters for Ibudilast by Treatment (PK Population)	X	X
35	Summary Statistics of Estimated PK Plasma Parameters for Bumetanide by Treatment (PK Population)	X	X
36	Summary Statistics of Estimated PK Urine Parameters for Ibudilast by Treatment (PK Population)	X	X
37	Summary Statistics of Estimated PK Urine Parameters for Bumetanide by Treatment (PK Population)	X	
38		X	X
39	KitAP Summary Statistics (Exploratory Population)	X	
40	OACIS-C Summary Statistics (Exploratory Population)	X	X
41	Summary of Responses for OACIS-C Assessment by Question (Exploratory Population)	X	X
42	Summary of Responses for OACIS-S Assessment by Question (Exploratory Population)	X	X
43	ABC-C Summary Statistics (Exploratory Population)	X	X
44	SRS-2 Summary Statistics (Exploratory Population)		
45	Summary of Responses for CSHQ Assessment by Question (Exploratory Population)	X	X
46	Lactate and Pyruvate Blood Level Summary Statistics (Exploratory Population)	X	X
47	Summary of Responses for CGI-S Assessment by Visit (Exploratory Population)	X	X
48	Summary of Responses for CGI-I Assessment by Visit (Exploratory Population)	X	X
49	Number and Proportion of Patients with Medical History Events (Safety Population)	X	X

Table No.	Table Title	Included in Final Tables	Shown in Appendix B
50	Number and Proportion of Patients Taking Concomitant Medications by ATC Level 4 and Preferred Term (Safety Population)	X	X

Listing No.	Listing Title	Included in Final Listings	Shown in Appendix B
DL1	Patient Disposition Data Listing	X	X
DL2	Demographics Data Listing	X	X
DL3	Adverse Events Data Listing	X	X
DL4	Vital Signs Data Listing	X	X

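### Exploratory Tables 38–48 cover only full-course patients, so those who stop or interrupt STP1 for intolerance leave the summaries that inform Phase 2 endpoint choice

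*SAP*

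**What the plan says.** Protocol 6.3.2 opens its definition with "The efficacy population will consist of all randomized patients who meet the inclusion/exclusion criteria" and adds that they must have "received full course of the study drug as per randomization, have completed the main relevant visits" and be free of major violations that make the data unreliable. SAP 2.2 repeats this under the name Exploratory population, again requiring that patients "received full-course of the study drug as per randomization", and states: "Analyses of PD data will be performed on the Exploratory population". The table list in SAP 8.0 labels Tables 39–48 accordingly, for example "ABC-C Summary Statistics (Exploratory Population"; the title of Table 38 is blacked out in the list, but its shell carries the same label. SAP 2.3 adds that "all analyses will be based on the observed data (i.e., complete case analysis".

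Protocol 3.1.2 ends dosing when an adverse event is judged related to study drug "and is graded as severe or SAE, no further doses of study drug will be administered". It also discontinues patients who meet listed vital-sign, ECG, laboratory or orthostatic criteria. Protocol 4.7.1.1 allows patients who stop STP1 to be replaced. Protocol 4.6.2.3 asks those who discontinue early to return on Day 28.

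**The concern.** Taking the full course and completing the visits are events after randomisation, and some of the reasons for failing them are effects of treatment. A patient taken off STP1 under protocol 3.1.2 cannot have had a full course, so that patient's scores enter none of Tables 38–48. The blinded review in SAP 2.2 concerns protocol violations and does not bring such a patient back.

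The exploratory objectives (protocol 2.3) are worded as effects relative to placebo. Protocol 3.2 and 6.3.2 say the results will feed the Phase 2 design and the choice of endpoints. A table that shows only patients who tolerated the drug answers a narrower question than the objective asks, and the gap can matter in groups this small.

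**Working it through.** **1. The plan's own figure.** The synopsis gives the basis for enrolment as "Assuming a dropout rate of approximately 20" per cent, with up to 16 completers. 16 / (1 − 0.20) = 20, so the stated maximum reproduces. This is dropout from any cause, with replacement, so it is not a rate of stopping for intolerance.

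**2. Interruptions.** Dosing is twice daily on Days 1–13 and once on Day 14: 2 × 13 + 1 = 27 doses. Protocol 3.1.2 describes a 48-hour stop for transient gastrointestinal pain as common. That is about 4 doses, leaving 23 / 27 = 85%. Neither document says what share of doses counts as a full course. Read literally, such a patient is excluded even after resuming and attending Day 14.

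**3. Size, on assumed inputs.** The documents give no stopping rate for STP1, so take q = 5% to 30%. The only adverse-event dropout rate for a component is 6/21 = 28.6% (protocol 1.5.2). It comes from children and adolescents on 2 mg twice daily of the diuretic alone, and serves only as an upper reference.

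- Chance that at least one of n STP1 patients leaves the tables: 1 − (1 − q)^n. For q = 0.20 and n = 6: 1 − 0.80^6 = 1 − 0.262 = 0.738.
- Shift of the STP1 mean. If completers average m_c and those who stop average m_s, the all-treated mean is (1 − q)m_c + q·m_s. The completer mean differs from it by q(m_c − m_s) = q·d. Assume d = 0.5 to 1.0 SD.

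| q | n = 3 (minimum at highest dose) | n = 6 (one cohort) | n = 12 (both cohorts) | shift q·d (SD) |
|---|---|---|---|---|
| 5% | 0.143 | 0.265 | 0.460 | 0.025–0.05 |
| 10% | 0.271 | 0.469 | 0.718 | 0.05–0.10 |
| 20% | 0.488 | 0.738 | 0.931 | 0.10–0.20 |
| 30% | 0.657 | 0.882 | 0.986 | 0.15–0.30 |

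With 3 patients at the highest dose, one stop removes a third of the group. As a responder example, suppose 2 of 6 treated patients respond on OACIS-C, and 2 non-responders stop early but attend Day 14. The full-course table shows 2/4 = 50%; all treated shows 2/6 = 33%.

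**4. Data available for those who leave.** On the schedule in protocol Appendix 1:

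- ABC-C, CGI-S, CGI-I, CSHQ, KiTAP and the cognitive battery are collected on Days 14 and 28.
- Lactate and pyruvate are part of blood chemistry (protocol 4.6.1.5), drawn on Days 7, 14 and 28.
- OACIS after baseline is Day 14 only, and so is SRS-2. Protocol 4.6.2 still lists SRS-2 at Day 28, and SAP 1.2 keeps that visit for patients enrolled under Versions 2–4.

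**5. CSHQ.** The Statistical Methods entry of the protocol synopsis names CSHQ change from baseline as a safety and tolerability measure in all treated patients. SAP Table 45 uses the Exploratory population. The two do not agree.

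**The case against.** The strongest reply is that little is hidden. The by-patient listings DL21–DL30 are set in the Safety population, Figure 13 plots L:P for the same set, and DL40 lists everyone excluded from the Exploratory population. With 16 to 20 patients, a reader can see every treated patient's scores. Adverse events and discontinuations (Tables 4–14) use the Safety population, and disposition (Table 1) uses all enrolled patients. EEG and eye tracking are left to a separate plan. All of this stands: the point is confined to Tables 38–48 and leaves the primary objective untouched.

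Second, the analysis is descriptive by group, with no difference estimate, interval or test, and protocol 6.3.2 and 6.5 say the study is not designed for efficacy. A full-course set is a reasonable way to look for a pharmacological signal. That supports keeping it, but not having it as the only tabulated set when the objectives are framed against placebo.

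Third, an all-treated run recovers only part of the data. Someone who left before Day 14 adds nothing to the Day 14 rows and mainly contributes a Day 28 value off drug. That is correct, with one qualification: the last scheduled dose is on the morning of Day 14, so Day 28 is off drug for completers too, and early stoppers differ in having been off longer. The larger gain is patients who paused or missed doses and still attended Day 14.

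**Conclusion.** The point holds for the summary tables. Following the plan as written removes patients who stop STP1 for intolerance from all of Tables 38–48, and probably those who interrupt it. This may bias the informal comparison with placebo if stopping is more frequent on STP1 and related to outcome. The documents establish neither condition, so the 0.025 to 0.30 SD range is an illustration on assumed inputs. It also treats every patient who stops as having an observable value, which step 4 shows is only partly so. The CSHQ conflict needs no assumption.

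Two stronger readings are not supported:

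- A reader might infer that the rule favours STP1. It applies equally to both arms, and violation-based exclusions are decided blind. The direction is plausible but not shown.
- A reader might take 20 × 0.20 = 4 patients lost, or 1/4 = 25% of the placebo group per exclusion, as the size of the bias. The 20% is all-cause and offset by enrolling 20 and by replacement. Four placebo patients belong to the 16-completer target (protocol 6.1); 20 randomised 3:1 would give 15 + 5. Losing a placebo patient costs precision and does not measure the effect of dropping patients who tolerate STP1 poorly.

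This is worth correcting before unblinding, but it does not threaten the study's safety conclusions.

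**What to change.** - Produce Tables 38–48 in all treated patients with a baseline value (where the endpoint has one) and at least one post-baseline value, on observed data and as treated. Keep the full-course set alongside as supportive.
- Mark Day 28 values from early stoppers as off-drug, ideally with days since last dose.
- Present CSHQ in the Safety population to match the synopsis, including the change from baseline it names; the Table 45 shell shows only response counts by question.
- State, before unblinding, what share of the 27 scheduled doses counts as a full course for the supportive set.

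The cost is a second run of these tables and a short SAP revision, with no new visits, data or patients. The gain is limited for endpoints assessed only at Day 14 (OACIS, and SRS-2 on the current schedule) when the patient left before that visit.
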